been effective in smoking cessation treatment⁹³ and could be added to TAUs targeting other substances of abuse. A new application of the iTBS intervention is proposed here and is modeled after the rTMS implementation designed to reduce symptoms of depression. For depression, positive effects occur after 26-28 NIBS sessions^{94, 95}. To decrease time to positive effects, multiple rTMS sessions have been implemented in a single day. As many as 10 daily sessions⁹⁶, though more modest schedules of 2 sessions per day for 10 days⁹⁷ to 4 sessions per day for 5 days⁹⁸, have also been implemented. By implementing multiple treatment sessions in a single day, the scheduled duration of treatment is condensed. This condensed schedule could increase retention rates compared to longer treatment schedules and be easier to implement in clinical settings. A single study has implemented multiple NIBS sessions a day in a sample of cocaine users⁹². In that study, participants received two 120 second trains of cTBS with a 60 second break between trains over mPFC. A total of 3,600 cTBS pulses were administered over a 5-minute period. This protocol reported no adverse events and was effective in reducing cocaine craving while administering 600 more pulses than a traditional rTMS session (3,000 pulses) in much less time (5 minutes) than a traditional 30 minute rTMS session. The treatment reduced resting activity in the ventral striatum while also reducing subjective cocaine craving. Another group administered 3 iTBS sessions (1,800) pulses with only a 15-minute break between trains of 600 pulses^{99, 100}. This group identified no benefit to administering subsequent iTBS sessions before after-effects had dissipated from a previous administration. To account for after-effects between iTBS administrations, a break of at least 30 minutes is necessary. Based on the above, we propose administering 3 iTBS sessions totaling 1,800 pulses per day in a cocaine dependent sample. However, tolerability of multiple daily iTBS sessions within CD participants will be first established in a Pilot before initiating the Expanded Feasibility Study.

D. Severe Acute Respiratory Syndrome Coronavirus 2 (SARS-CoV-2): Risk Minimization and Data Integrity

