Urine Benzoyllecgonine Test. Urine samples will be collected from all CD participants and will be used in the implementation of CM. These samples will be collected under observation of a same-sex observer to confirm its validity. The urine toxicology analysis will be used to assess a broad range of prescription and nonprescription drugs by metabolite quantitation using a dip card, which is a one-step urinalysis immunochromatography drug rapid test (5 minutes), to assess recent use of drugs of abuse. It is designed for qualitative screening of cocaine metabolite in human urine specimens and provides a preliminary analytical test result for on-site testing. Additionally, the urine sample, when positive for cocaine, will be sent for quantitative 'additional use' analysis in the NIDA-IRP Translational Analytical Core (TAC), for implementation of CM. Missing samples will be considered positive. Completion time: ~10 minutes.

3. MRI Scan Sessions

On all days with an MRI scan, participants are expected to complete several clinical assessments as well as experimental tasks (see Figures 1 and 2 for graphical summary). However, availability of staff, facilities and participant schedule may require some flexibility in timing and measures performed in the outline below. CD participants will be scheduled to complete all 8 scans described below and HC participants will be scheduled to complete up to scan 4. Because HC participants will have a within participant active vs sham manipulation (described below), they will complete scans 3 and 4 twice; once with active and once with sham iTBS (see Figures 1 and 2).

Pre-scan Assessment. Participants will complete a nursing assessment (as described above) upon arrival for each scan session. nursing assessments that occur on scan days will include an MRI safety screening.

Pre-scan task practice. Prior to each scan, participants will be reacquainted with the task instructions and will complete brief training runs. Completion time: ~30 minutes.

Self-report measures. At each scan session, participants will be administered several brief measures to assess current arousal (modified version of the PANAS), mood (POMS) and other withdrawal symptoms (CD participants only; Cocaine Craving Likert Scales, Cocaine use, Pattern, and Withdrawal Questionnaire). These measures will be administered on a computer in a private area. Completion time: ~30-40 minutes.

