Drug Use. A urine sample will be collected from CD participants which will be used to implement CM.

Scan 1. Completed on visit 1: Localizer (~ 1 min); Structural scan (~ 5 mins); MID (~ 30 mins); Flanker (~25 mins); N-Back Task (~ 10 mins); SSRT (~ 15 mins); Approximately 2 hours.

Scan 2. Completed on visit 2: Localizer (~ 1 min); DTI (~ 10 mins); Resting (~ 10 mins); Amygdala task (~7 mins); ASL (~10 mins); Approximately 1.5 hours.

Scan 3. Completed on visit 3 (preceding the first iTBS treatment on the first treatment day): Localizer (~ 1 min); ASL (~ 10 mins); Resting (~ 10 mins); SSRT (~ 15 mins); Amygdala (~7 mins); Cue Reactivity (~ 15 mins); Approximately 1 hour.

Scan 4. Completed on visit 3 (following the last iTBS treatment on the first treatment day): Localizer (~ 1 min); ASL (~ 10 mins); Resting (~10 mins); SSRT (~ 15 mins); Amygdala (~7 mins); Cue Reactivity (~ 15 mins); ASL (~ 10 mins). ASL at the beginning and end of this scan session will measure trajectory of change of blood flow/neuronal activity over time after the TMS session. Approximately 1.5 hours.

Scans 5 & 7. Completed on visits 19 and 36: Localizer (~ 1 min); ASL (~ 10 mins); Resting (~10 mins); Amygdala (~7 mins); Cue Reactivity (~15 mins); Flanker (~25 mins); N-Back (~10 mins); Approximately 2 hours.

Scans 6 & 8. Completed on visits 19 and 36: Localizer (~ 1 min); Structural (~5 mins); DTI (~10 mins); SSRT (~15 mins); MID (~30 mins). Approximately 2 hours.

Debriefing. At the end of the scanning session there will be a debriefing period for discussion of questions and issues related to the day's tasks. They will also schedule a time for their next session.

4. iTBS Sessions

HC participants will be scheduled for 2 days of iTBS - 1 DAY of active iTBS and 1 DAY of sham iTBS, with at least a 60-minute interval between sessions and at least 1 week between DAY. The order of these days will be counterbalanced.

CD participants will be scheduled for 10 days of iTBS treatment and randomly assigned to receive either active or sham iTBS. Participants will initially be scheduled to complete all treatment DAYS in 2-weeks whenever possible, however, they will have up to 3 weeks to complete the 10 DAYS of treatment.

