Questionnaires/Behavioral measures: Some or all assessments and/or tasks may be completed remotely via a secure platform approved by NIDA-IRP's ISSO, or via a secure web link set up by the NIDA-IRP BIS team. For this option, participants must have use of a private space with secure internet connection. Participants will be instructed how to complete the assessments/tasks via phone or encrypted video chat program approved by NIDA IRP's ISSO.

SARS-CoV-2 antibody testing: COVID-19 has been reported to be capable of producing long-lasting neurological effects that might include subtle cognitive deficits (Ritchie et al 2020). The prevalence of such deficits, if they exist, is unknown. Therefore, we will assess SARS-CoV-2 antibodies in order to assess for possible effects. How this data will be used will depend on the number of antibody-positive participants in the final cohort as well as future publications on the impact of antibody status on the data being gathered. We will not use antibody testing for diagnosis or treatment of participants, and participants will not be informed of the results, as they have no clear clinical significance and could be misinterpreted. We may collect about 1 mL of blood or up to 2mL of saliva for antibody testing. We may collect this sample at the first visit that includes an MRI scan and at other visits including an MRI scan if the participant has not been recently tested for COVID-19, and/or if subsequent scan(s) are more than a few weeks apart. If a participant has a documented history of positive COVID-19 diagnostic or antibody test, the MAI will determine whether antibody testing under this protocol is necessary.

ii. Experimental Measures

1. Imaging Measures

MRI Scanner Sessions. The total time that participants will be inside the scanner each session is approximately 2 hours (note: all times approximate and order of scans generally fixed but may be switched in the event of instrument problems or participant compliance).

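### The interval from the last iTBS session to scan 4 is neither capped nor used in the analysis, and the listed pre-scan steps can delay the acute measurement

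*Combined protocol and SAP*

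**What the plan says.** Section III.E (Experimental Design) compares scan 4 with scan 3 to assess the acute effect of iTBS. Section III.G.i.3 (MRI Scan Sessions) places scan 4 as follows: "Completed on visit 3 (following the last iTBS treatment on the first treatment day". It gives no latest start time.

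The same section lists the steps around every scan. On practice: "Prior to each scan, participants will be reacquainted with the task instructions and will complete brief training runs", with a stated completion time of about 30 minutes. On questionnaires: "At each scan session, participants will be administered several brief measures to assess current arousal", followed by mood and, for cocaine-dependent (CD) participants, craving and withdrawal, with this duration: "These measures will be administered on a computer in a private area. Completion time: ~30-40 minutes". Whether the questionnaires come before or after the scan is not stated. The section also says: "However, availability of staff, facilities and participant schedule may require some flexibility in timing and measures performed in the outline below".

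Section III.G.ii.1 (Imaging Measures) describes the "order of scans generally fixed but may be switched in the event of instrument problems or participant compliance". Scan 4 has ASL at both ends, to follow how blood flow changes after stimulation.

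On after-effects, section I.C says: "To account for after-effects between iTBS administrations, a break of at least 30 minutes is necessary". The study itself spaces sessions by at least 60 minutes (section III.A). Section III.G.vi (Statistical Analysis) does not mention the interval from stimulation to scan.

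**The concern.** An acute contrast depends on when it is measured relative to stimulation. The plan accepts this for blood flow, since it repeats ASL at the end of scan 4. The pilot also tied its recruitment curves to iTBS: before, immediately after, and at least 60 minutes after (section II.E.ii.3). The resting and task runs of scan 4 have no such anchor.

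Read in the order listed, the pre-scan steps put practice, and perhaps questionnaires, between the coil and the scanner. If the effect fades over that period, the active-sham difference at scan 4 shrinks in both CD participants and healthy controls (HC), and a null result for Aim 2a or Hypothesis 3 becomes hard to interpret. Without a logged lag, this could not be examined afterwards.

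**Working it through.** **Inputs** (section III.G.i.3). Scan 4 runs in listed order: localizer 1 min, ASL 10, resting 10, SSRT 15, amygdala 7, cue reactivity 15, second ASL 10. Practice is about 30 min and self-report about 30-40 min.

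**The plan's own totals.** Scan 3: 1 + 10 + 10 + 15 + 7 + 15 = 58 min, which agrees with the stated hour or so. Scan 4: 58 + 10 = 68 min against a stated 1.5 hours, so 90 - 68 = 22 min are not itemised. The 30-minute spacing figure in section I.C has no inputs from which to recompute it.

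**Start times.** Start of a run = preparation time + durations of the runs before it. Transfer, positioning and post-stimulation checks are set to zero, so these are lower bounds for each scenario.

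| Run | No delay | Practice only (30) | Practice + self-report, summed by instrument (HC 40 / CD 50) | Practice + self-report as stated (60-70) |
|---|---|---|---|---|
| First ASL | 1 | 31 | 41 / 51 | 61-71 |
| Resting | 11 | 41 | 51 / 61 | 71-81 |
| SSRT | 21 | 51 | 61 / 71 | 81-91 |
| Amygdala | 36 | 66 | 76 / 86 | 96-106 |
| Cue reactivity | 43 | 73 | 83 / 93 | 103-113 |
| Second ASL | 58 | 88 | 98 / 108 | 118-128 |

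The fourth column uses the single-instrument times in section III.G.i.2: modified PANAS under 5 min, POMS about 5, and the cocaine use questionnaire about 10 in CD only. The craving scales have no stated time. That gives roughly 10 min in HC and 20 min in CD, less than the 30-40 min stated for the battery.

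**Order.** In every column cue reactivity starts 10 + 15 + 7 = 32 min after resting.

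**What delay could cost (assumption only).** The documents give no decay curve. Suppose the effect halves every h minutes, with h = 15, 30 or 60. A delay of d minutes then multiplies what remains by 0.5^(d/h). For the 30 min of practice this is 0.5^2 = 0.25, 0.5^1 = 0.50 or 0.5^0.5 = 0.71. If the effect is flat over the period, the factor is 1. A range from 0.25 to 1 means that the size is not known.

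**The case against.** Several points on the other side stand.

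- Only practice is expressly placed before the scan. Self-report is tied to the session, not to a side of the scan. The 60-70 minute sum is therefore one possible reading.
- A step that comes before the scan need not come after the last iTBS session. Practice could already fit in a gap of at least 60 minutes between sessions, and the flexibility wording allows this. Figures 1 and 2, which the section cites as a summary, were not available to me and may show the sequence.
- A reader might infer that after-effects end at 30 minutes, so that any later scan misses them. Section I.C does not say so. Its figure is a minimum spacing between sessions. The same section says the post-iTBS shift outlasts that of rTMS, and scan 4 follows three sessions.
- Even with no delay, amygdala and cue reactivity start at 36 and 43 minutes. Re-sequencing removes avoidable delay but does not bring every run inside 30 minutes.
- The timing rules are the same for active and sham, and scan 3 lists the same order through cue reactivity. Each construct's own pre-post contrast is therefore matched for position. The Statistical Analysis section treats the paradigms as separate primary analyses. Construct is confounded with elapsed time only in the secondary work that integrates them.
- The sample size rests on connectivity after the full treatment course, not on the acute contrast.

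The objection does not supply a cap on the interval, a fixed place for practice, or any use of the lag in the analysis.

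**Conclusion.** The gap is real and of moderate weight. The protocol permits a variable, uncapped interval before its only acute post-stimulation scan. If the stated practice follows the last session, all data runs begin at 31 minutes or later. If the full stated self-report also precedes the scan, resting begins at 71-81 minutes and cue reactivity at 103-113. These times rest on the listed run order and durations and on zero transfer time.

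The consequence is possible dilution of the acute contrast, of unknown size. A reader might go further and conclude that the acute effect will be missed, that active and sham are compared unfairly, or that the study cannot proceed without this change. The documents support none of these: they give no after-effect duration, the timing does not differ by arm, and the listed order need not be the order used.

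**What to change.** For scans 4, 4a and 4b:

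1. Do the task practice before the last iTBS session, in an existing interval of at least 60 minutes. The stimulation schedule does not change.
2. State where self-report falls relative to the scan. Keep mood and craving measures ahead of cue exposure, for example in the same earlier interval or as a short version just before the scan. Moving them after the scan would place them after the cocaine-cue run.
3. Go to the scanner once the required post-iTBS safety checks are done. Trails A and B stay as the protocol requires, before discharge.
4. Log minutes from the last pulse to the start of each run, and report them by construct and arm.
5. Pre-specify a sensitivity model of the acute contrast that includes this lag and its interaction with condition, since dilution would appear as an active-sham difference that shrinks with lag. In the secondary cross-paradigm analyses, state that the generally fixed order ties construct to elapsed time. Logging shows this but does not remove it.

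The cost is minor re-sequencing of one CD visit and two HC visits, plus one logged variable. If self-report moves to the earlier interval, it describes the participant's state before the third session rather than after it, and the report should say so.

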Protocol completers are defined as CD participants who complete 10 iTBS days of treatment within 3 weeks and visit 19 (first post-treatment scan day). CD participants who complete at least 5 iTBS treatment days in 3 weeks are eligible to begin with CM and follow-up visits. All study visits, including those with MRI scans, will be offered to these individuals as if they had completed all 10 iTBS treatment days. An HC participant is considered a protocol completer after completing all scheduled visits (baseline characterization visits and 2 iTBS treatment days with MRI scans).

Overall, CD participants will complete about 43 visits and HC participants 5 visits, with 8 and 6 MRI scans collected for CD and HC participants, respectively. Most of the visits for CD participants will be to collect urine samples and implement CM. The order of procedures completed during each visit may vary slightly, depending on availability of staff and other resources (mock scanner, MRI, study rooms, etc.).

Each study visit day will start with a brief nursing assessment that includes a urine sample for drugs of abuse, a breathalyzer, and vital signs. A urine pregnancy test for females will occur weekly during the iTBS treatment and any visit that includes an MRI scan thereafter. If breathalyzer is positive for alcohol participants may be rescheduled. In the event of a positive drug test, an interview to assess last drug use and a neuromotor assessment to test for acute intoxication will be performed. If participants test positive for drugs other than marijuana, based on MAI judgment, they may be rescheduled. If urine is positive for other illicit drugs, and if there are no known TMS contraindications, the participants may be allowed to participate at the discretion of the MAI. Otherwise, participants will be rescheduled. The CD group is expected to be current users and will likely test positive for illicit drugs. These procedures are designed to identify if CD participants are currently impaired and if HC participants have recently used illicit or licit drugs. Participants who smoke will be allowed breaks to smoke to preclude acute nicotine withdrawal. If a participant runs out of cigarettes, we will provide them on an as-needed basis to avoid withdrawal, which requires us to reschedule the visit. All study visits will take place at National Institute on Drug Abuse Intramural Research Program (NIDA-IRP).

1. Screening

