On iTBS days, participants will complete several questionnaires in addition to the iTBS treatments. During iTBS, participants will view cocaine cues (i.e., pictures; Appendix 25) in an attempt to control affective state across participants while also potentially eliciting activation in networks specifically related to cocaine use and substance abuse in general.

Pre-iTBS. Participants will complete a questionnaire about possible side-effects since the last iTBS session (the NIBS monitoring questionnaire) and a questionnaire about their affect (the modified version of the PANAS; see Appendix 1 & 15). Participants will also complete Trails A and B (Appendix 22) prior to and following iTBS administration each day. These assessments will also be collected at baseline prior to any TMS or iTBS administration to assess a true baseline measure for each participant. Also, measures of mania (Young Mania Rating Scale [YMRS]; Appendix 23), suicidality (Columbia-Suicide Severity Rating Scale: Baseline [C-SSRS]; Appendix 24) and depression (MADRS¹¹²; Appendix 14) will be collected prior to the first iTBS session in CD.

iTBS Session. Resting motor threshold will be determined daily, as described below. Recruitment curves will be measured during orientation (HC and CD), and in the CD group, before the first iTBS administration on iTBS day 1, after the last iTBS administration on iTBS day 10, and each of the follow-up visits with an MRI scan. Approximately 1 hour.

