Post-iTBS. At the end of the visit, participants are asked to fill in a questionnaire about possible side-effects (the NIBS monitoring questionnaire), a questionnaire about their affect (the modified version of the PANAS; see Appendix 1 & 15), questionnaires assessing the blind will be administered (Appendix 46), and an assessment of pain will be administered (Appendix 46). The iTBS administrator will also fill out an assessment of the blind (Appendix 47). Questions about blinding and pain levels will be asked of the participant after the last iTBS session. Questions about blinding will be asked of the TMS operator after the last iTBS session. Participants will also complete Trails A and B (Appendix 22) after the final iTBS administration each day, prior to discharge. After the final iTBS session (i.e., on Day 10, prior to discharge), measures of mania (Young Mania Rating Scale [YMRS]; Appendix 23), suicidality (Columbia-Suicide Severity Rating Scale: Baseline [C-SSRS]; Appendix 24) and depression (MADRS¹¹²; Appendix 14) will be collected. Contact attempts will be made by phone 1-3 days after the last iTBS session to assess any acute behavioral or health related changes from treatment (Appendix 1).

5. Post-Treatment Follow-Up

Ongoing follow-up will be attempted for 24-weeks post-treatment and will include urine samples for implementation of CM, as outlined in Table 1, and assessments of substance use (participants may repeat some or all characterization measures and assessments of drug use). MRI scans will be performed about one month and three months after the start of iTBS treatments (on approximately visits 19 and 36) to assess neural plasticity related to abstinence, reduction, or continuation of drug use post-treatment. The ASI will be scheduled to be completed within 1-week of all follow-up

visits that include an MRI scan, along with the three mood measures (YMRS, MADRS and C-SSRS). ASI will also be completed at the final visit of the study. The first 12-weeks post-treatment follow-up appointments will be in-person. The next 12-weeks will consist of once-a-week phone contact attempts and once-a-month in-person visits to assess drug use post-treatment. Additional attempts will be performed only through means approved by the participant. These may include such alternative methods as text and e-mail if phone contact is not successful.

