If a participant experiences somatic or psychological symptoms that interfere with his/her ability to participate then he/she will be discharged from the study. The most frequent symptom is pain over the area of stimulation which could interfere with participation in the study. DLPFC stimulation has rarely been associated with mania. The investigators will monitor participants for changes in mood and may discharge a participant at any time if they believe that it is in the best interest of the participant. Participants who fail to tolerate iTBS at 100% of RMT during their toleration session will be discharged from the study. Those with RMT over 83% of MSO will be discharged as the recruitment curves require administering pulses up to 120% RMT, which is only possible if RMT is 83% or less.

7. Participant Monitoring

The NIBS monitoring questionnaire (Appendix 1), Trails A and B (Appendix 22), and staff observation and interactions with participants will be assessed daily. A NIDA-IRP physician or Physician's Assistant knowledgeable about iTBS will be immediately available in the building whenever iTBS is administered and will be available by telephone or pager 24 hours a day for consultation or in the event of a medical emergency. If immediate medical intervention is required, the participant will be referred to an appropriate medical facility. Information on all adverse events will be cumulated and reported to the NIH IRB with each continuing review application. Unexpected or serious adverse events (defined in accordance with NIH and NIDA IRP policy) will be promptly reported to the NIDA Clinical Director and IRB in accordance with NIH and NIDA IRP policy (see DSMP below).

Seizure monitoring procedures: Participants will be monitored throughout each iTBS session for signs of seizures such as involuntary muscle movements or loss of consciousness. In the event of a seizure, staff will have immediate access to life support equipment and anti-seizure drugs. In the event of a seizure, the procedure outlined below¹²⁹ will be followed:

1. Protect patient's head and limbs from injury.
2. Ensure an adequate airway.
3. Call 911 to have the patient transferred to Johns Hopkins emergency room, if the seizure requires medication intervention to resolve or is otherwise clinically indicated.
4. Observe Patient for:
 - a. Initial movements/ sensations.
 - b. Progression of movements.
 1. Change in respiratory status
 2. Skin color
 3. Incontinence

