Nonetheless, there is a single published report in a sample of participants with major depression where functional connectivity was measured pre- and post-rTMS treatment¹⁶⁶. In this report, the mean functional connectivity pre-TMS (0.38 z-scored connectivity) was greater than post-TMS (0.22 z-scored connectivity) with an average standard deviation of 0.17 z-scored connectivity. We calculated the effect size to be 0.91. This effect size is likely unrealistically high due to 'double-dipping' in their analyses¹⁶⁷, a small sample size, and publication bias toward significant effects, all of which affect the effect size calculation and generalizability.

To better assess a more realistic effect size based on these findings, we simulated an effect size (N =10,000) based on the published means and standard deviations. The effect size that falls 1 standard deviation below the mean was 0.64. This effect is remarkably close to a published report comparing functional connectivity between healthy controls and cocaine users⁴⁴ without a TMS intervention (calculated effect size of 0.67).

Together, when assessing functional connectivity differences post-iTBS treatment between active and sham groups, we conservatively select an effect size 0.65 to capture a reliable effect while reducing the likelihood of committing a Type II error and a power level (1- β) of 0.8 to achieve an appropriate balance between the ability to detect significant differences and the number of participants needed. Therefore, for power analysis calculations (i.e., Statistical Analysis Plan), we anticipate a mean functional connectivity measure post-iTBS for the sham group to be 0.210 z-scored connectivity and active group to be 0.405 z-scored connectivity with a standard deviation of 0.299 z-scored connectivity, which produces an effect size of 0.65 and an estimated sample size needed per group to be 30 with a one-tailed *t*-test assuming a *p*-value of .05. We anticipate approximately 60% retention rate by visit 19, based on previous NIDA protocols. Therefore, 100 CD participants will be recruited at baseline, 45 active and 45 sham iTBS, to acquire the necessary 30 participants in each group for analysis.

IV. COLLECTION AND STORAGE OF HUMAN SPECIMENS OR DATA

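### The end-of-treatment mania, suicidality and depression scales are scheduled for iTBS Day 10, so cocaine-dependent participants who stop earlier have no scheduled end-of-treatment rating on them

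*Combined protocol and SAP*

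**What the plan says.** Four parts of the protocol bear on this, all for CD participants in the Expanded Feasibility Study.

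- **Baseline** (III.G.i.4, Pre-iTBS): the YMRS, C-SSRS and MADRS "will be collected prior to the first iTBS session in CD".
- **End of treatment** (III.G.i.4, Post-iTBS): "After the final iTBS session (i.e., on Day 10, prior to discharge), measures of mania (Young Mania Rating Scale", followed by the C-SSRS and MADRS.
- **Follow-up** (III.G.i.5): the scales are repeated within a week of all follow-up "visits that include an MRI scan, along with the three mood measures (YMRS, MADRS and C-SSRS"). The first of these scans is at visit 19.
- **Early stoppers** (III.G.i): "CD participants who complete at least 5 iTBS treatment days in 3 weeks are eligible to begin with CM and follow-up visits". For this group, "All study visits, including those with MRI scans, will be offered to these individuals as if they had completed all 10 iTBS treatment days".

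Section III.G.iii.6 adds: "The investigators will monitor participants for changes in mood and may discharge a participant at any time". It names no rating at that exit. The Post-iTBS paragraph also provides a safety call that depends on the last session and not on a day number: "Contact attempts will be made by phone 1-3 days after the last iTBS session to assess any acute behavioral or health related changes". That call uses the side-effect questionnaire in Appendix 1.

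**The concern.** The plan expects some participants to stop early. It sets a 5-day threshold for moving on to contingency management and follow-up. In III.G.vi it says that, if most participants fall short of 10 days, everyone with five days would be considered in the final analysis. The end-of-treatment mood ratings do not follow that logic, because they are fixed to a day that early stoppers never reach.

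The participants without a rating are unlikely to be a random subset. Mood change is one of the reasons the protocol gives for ending participation, so a missing rating may be related to the value it would have had. Aim 5 is to monitor the safety of iTBS in cocaine-dependent people. An end-of-treatment comparison of the arms on these three scales would describe only those who completed the course.

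**Working it through.** The documents give no figure for missing mood ratings, so there is none to reproduce. The check is of the schedule, followed by a range for the number affected.

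**1. Scheduled YMRS, C-SSRS and MADRS, by iTBS days received**

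| iTBS days | Before first session | End of treatment | Near visit-19 scan |
|---|---|---|---|
| 10 | yes | yes | yes |
| 5 to 9 | yes | none scheduled | yes, if they attend |
| 1 to 4 | yes | none scheduled | not eligible under the 5-day rule |

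No section adds the scales at early termination or discharge.

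**2. Delay for those with 5 to 9 days**

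Assumptions: iTBS runs on weekdays from Monday of week 2 to Friday of week 3, and early stoppers keep the same visit calendar. Table 1 has three urine samples a week from week 4, so visits 13-15 fall in week 4, visits 16-18 in week 5, and visit 19 opens week 6. This agrees with III.E, which puts the visit-19 scans in week 6.

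- Day 10 (Friday, week 3) to Monday, week 6: 3 + 14 = 17 days.
- Day 9 (Thursday, week 3): 17 + 1 = 18 days.
- Day 5 (Friday, week 2): 3 + 21 = 24 days.
- Allowing a week either side of the scan: from 18 - 7 = 11 to 24 + 7 = 31 days.

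A course spread over the permitted 3 weeks would change these figures. Section V.B.ii.6 describes the psychiatric side-effects in its rTMS case reports as transient, so a first rating some 11 to 31 days after stopping could miss a similar change.

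**3. Number affected**

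Inputs: 45 CD participants per arm (III.E), and "We anticipate approximately 60% retention rate by visit 19" (III.G.vi).

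- Not retained to visit 19: 45 × (1 - 0.60) = 18 per arm, or 36 of 90.
- On the 30 of 45 per arm that the plan wants for analysis: 45 - 30 = 15 per arm.

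This loss includes people who leave at orientation and people who leave between Day 10 and visit 19. The documents do not divide it. If none of it falls before Day 10, 0 per arm lack the rating; if all of it does, 18 per arm (40%) do. The upper end takes retained to mean completed, that is, 10 iTBS days plus visit 19, which is how III.G.i defines a completer. It also assumes equal loss in the two arms.

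**4. Whether other measures fill the gap**

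- NIBS monitoring questionnaire (each iTBS day, and at the 1-3 day call): side-effects.
- Modified PANAS (each iTBS day): its stated purpose is one item on feeling detached (III.G.i.2).
- Trails A and B (each iTBS day): cognition.
- Staff observation and adverse-event reporting: may record an episode, but give no score.
- POMS: tied to scan sessions, so none is scheduled between the first iTBS day and visit 19.

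All of these are useful. None gives an end-of-treatment mania, suicidality or depression score that can be compared between arms.

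**The case against.** The strongest reply is that the safety system does not rest on these scales. The named safety endpoints (IV.C.i and IX.C.i) are seizures, Trails B and clinically significant adverse events likely related to iTBS, each compared between arms by chi-square. A related mood episode that needed referral would count there on whatever day it occurred. This stands, and it limits the point to the three scales.

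It can also be said that the final session means each participant's own last session, with Day 10 as the nominal case. That reading is possible, but the text equates the two. The same paragraph ties the phone contact and the blinding questions to the last session with no day number. At best the wording is ambiguous.

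Four stronger inferences are tempting, and the documents do not support them.

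- **Early stoppers have no safety assessment at the end of treatment.** The daily measures and the 1-3 day call do not depend on reaching Day 10.
- **The three scales are seen only in those who complete 10 days.** They recur near the follow-up scans, which are offered to those with 5 to 9 days.
- **The active arm will look safer than it is.** Informative missingness is plausible, but its size and direction by arm are unknown, and the named safety endpoints are unaffected.
- **The rTMS case reports in V.B.ii.6 show on which iTBS day mood change would appear.** They involve other patients, sites and schedules, and section V.B.ii.6 itself places the risk mainly in people with existing psychiatric morbidity. Session counts do not carry over to iTBS days.

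**Conclusion.** The point holds for the three scales. Followed as written, the plan schedules no end-of-treatment YMRS, C-SSRS or MADRS for CD participants who stop before Day 10, including any discharged for mood change, and no rating after baseline for those with fewer than 5 days. An end-of-treatment comparison of the arms on these scales would be a comparison of people who reached Day 10.

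The size is uncertain. Between 0 and 18 of 45 per arm could be affected, and 18 should not be read as the expected number. For those with 5 to 9 days, the delay of about 11 to 31 days rests on the weekday calendar assumed above. This is a gap in a supporting safety measure under Aim 5. It does not undermine the imaging analysis or the stop rules, but it should be closed because doing so is cheap.

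**What to change.** In III.G.i.4, Post-iTBS, replace the parenthesis that names Day 10 with: *on the participant's last iTBS day, whether Day 10 or earlier, prior to discharge*.

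Add a fallback: if the stop is not known that day, attempt the three scales at or around the 1-3 day contact, in person or through the remote platform already allowed in III.G.i.5. That text requires an approved secure platform and a private space, and it does not clearly cover interview-based ratings, so the amendment should say that it does.

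In III.G.vi, state that the three scales will be summarised by arm for all CD participants who received any iTBS, with the number missing at each time point.

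While the sentence is open, reconcile the C-SSRS version: it names the Baseline form after treatment, whereas the Pilot section uses the since-last-visit form at that point.

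The cost is a wording amendment and one extra assessment for early stoppers only. The protocol's own completion times are under 15 minutes each for the YMRS and C-SSRS and under 10 for the MADRS, so 15 + 15 + 10 gives less than 40 minutes. Some ratings will be done remotely, and some will not be obtainable from people who simply stop attending. The change adds no ratings during treatment for those who continue, and it alters no treatment or stopping rule.
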